4 STUDY POPULATION SELECTION

4.1 Study Population

Approximately 18 healthy subjects who consent to participate in this study will be enrolled.

4.2 Inclusion Criteria

Each subject must meet the following criteria to be enrolled in this study.

1. Subjects who are between the ages of 18 to 55 years, inclusive at time of consent, in good health based on medical history, physical examination (PE), electrocardiogram (ECG), and routine laboratory tests, including blood chemistry, hematology, urinalysis, and drug screen.
2. Subjects with body-mass index (BMI) between 18.0 kg/m² and 32.0 kg/m² at screening, inclusive.
3. Subjects who are non-smokers for at least 6 months prior to screening.
4. Subjects with adequate venous access at multiple sites in both arms.
5. Subjects who are willing to refrain from smoking, alcohol, grapefruit, grapefruit juice or related products, caffeine consumption (including chocolate), and strenuous exercise within 72 h prior to first dose and through the end of the study.
6. Male subjects who are surgically sterile or agree to refrain from donating sperm and use appropriate birth control when engaging in sexual intercourse for a period of 30 days after discharge from the clinic. Appropriate birth control methods include condoms with spermicide, female partner's use of diaphragm with spermicide, female partner's use of stable oral, implanted, or injected contraceptive hormones, or with an intrauterine device.
7. Female subjects of childbearing potential who are willing to use an adequate method of contraception and to not become pregnant for the duration of the study. Adequate methods of contraception for female subjects of childbearing potential include bilateral tubal ligation, intrauterine device, diaphragm with spermicide and male partner's use of male condom with spermicide. Female subjects who are surgically sterile (i.e. have undergone partial or full hysterectomy, or bilateral oophorectomy) or postmenopausal (absence of menses greater than 12 months and age > 50 years) are eligible if they test negative on the urine pregnancy test.
8. Subjects who are willing and able to be confined to the clinical research facility and comply with study activities and restrictions as required by the protocol.
9. Subjects who have the ability to comprehend and who are willing to provide written informed consent in accordance with institutional and regulatory guidelines

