Period 2, Treatment A: Subjects will be admitted on Day 14. On Day 15, subjects will start to receive once daily oral dose of 20 mg bexagliflozin for 8 days; a single dose of 0.5 mg digoxin will be co-administered with bexagliflozin on Day 17. Blood samples for PK will be drawn at pre-dose and at 0.5, 1, 1.5, 2, 3, 4, 6, 8, and 12 hours (h) on Day 17, 24 h (Day 18), 48 h (Day 19), 72 h (Day 20), 96 h (Day 21), and 120 h (Day 22) after administration of digoxin. Subjects will be discharged from the clinic on Day 22.

Study Population: Approximately 18 healthy subjects are planned.

Diagnosis and Main Criteria for Inclusion:

1. Subjects who are between the ages of 18 and 55 years, inclusive, in good health based on medical history, physical examination, ECG, and routine laboratory tests (blood chemistry, electrolytes, hematology, lipids, urinalysis, and drug screen)
2. Subjects with body-mass index (BMI) between 18.0 kg/m² and 32.0 kg/m², inclusive
3. Subjects who are not surgically sterile must agree to use appropriate birth control when engaging in sexual intercourse for a period of 30 days after discharge from the clinic
4. Subjects who are non-smokers for at least 6 months prior to screening

Test Product; Dose; and Mode of Administration:

Bexagliflozin Tablets, 20 mg, oral administration

Reference Therapy; Dose; and Mode of Administration:

Digoxin Tablets, 0.5 mg, oral administration

Duration of Treatment:

Each study subject will receive a total of 8 doses of bexagliflozin (20 mg) and 2 doses of digoxin (0.5 mg) during 2 treatment periods with a study duration of up to 46 days, including screening and washout periods.

Pharmacokinetic Variables:

The following PK parameters of digoxin, if possible, will be determined after each subject is dosed with either digoxin alone, or the combination of digoxin and bexagliflozin.

C _{max}	Maximum observed plasma concentration
t _{max}	Time of maximum observed plasma concentration
λ _z	Terminal elimination phase rate constant
t _½	Apparent terminal elimination half-life
CL/F	Apparent oral clearance
V _z /F	Apparent volume of distribution

AUC_{0-t} Area under the plasma concentration-time curve from Time 0 to Time t (time of last quantifiable plasma concentration)

$AUC_{0-\infty}$ Area under the plasma concentration-time curve from Time 0 to infinity

Safety Assessments:

Physical examinations

Vital signs

12-lead electrocardiograms

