6.7.3 Pregnancy

Women of childbearing potential (WOCBP) who are sexually active must use an effective method of birth control during the course of the study, in a manner such that risk of failure is minimized.

Before enrolling WOCBP in this clinical trial, investigators must review guidelines about study participation for WOCBP. The topics should generally include:

1. General information.
2. Informed consent form.
3. Pregnancy prevention information.
4. Contraceptives in current use.
5. Guidelines for the follow-up of a reported pregnancy.

Prior to study enrollment, WOCBP must be advised of the importance of avoiding pregnancy during trial participation and the potential risk factors for an unintentional pregnancy. The subject must sign an informed consent form stating the above-mentioned risk factors and that the consequences were discussed with her.

During the study, all WOCBP should be instructed to contact the investigator immediately if they suspect they might be pregnant (e.g., missed or late menstrual cycle).

If a subject or investigator suspects that the subject may be pregnant prior to investigational product administration, the investigational product administration must be withheld until the results of serum pregnancy tests are available. If the pregnancy is confirmed, the subject must not receive the investigational product and must not remain in or be enrolled in the study.

The investigator must notify the Medical Monitor within 3 working days of the receipt of information that any female subject who has become pregnant.

The investigator must record the event on the Pregnancy Surveillance Form and forward it to the sponsor's clinical or designated personnel.

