6.7.4.2 Follow-up of Post-Study Serious Adverse Events

SAEs that are identified on the last scheduled contact must be recorded on the AE CRF page and reported to Theracos according to the reporting procedures outlined in [Section 6.7.1](#). These may include unresolved previously reported SAEs, or new SAEs. The investigator should follow these subjects until the events are resolved, or the subject is lost to follow-up. Resolution means the subject has returned to the baseline state of health, or the investigator does not expect any further improvement or worsening of the subject's condition. The investigator should continue to report any significant follow-up information to Theracos until the event has been resolved.

Any new SAEs reported by the subject to the investigator that occur after the last scheduled contact, and are determined by the investigator to be reasonably associated with the use of the investigational product, should be reported to the Medical Monitor or the sponsor's designated personnel. These may include SAEs that are captured on follow-up telephone contact or at any other time point after the defined study period (i.e., up to last scheduled contact). The investigator should follow subjects with SAEs identified after the last scheduled contact until the events are resolved, or the subject is lost to follow-up. The investigator should continue to report any significant follow-up information to the Sponsor until the event has been resolved. This study requires that subjects be actively monitored for SAEs for at least 14 days after discharge from the study.

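### Minor: women's contraception duty ends with the study (for Group 2, on the last bexagliflozin dosing day), while men, and in the synopsis all non-sterile subjects, have 30 days after discharge

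*Protocol*

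**What the plan says.** Four places in the protocol bear on this.

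- **Section 4.2, the operative list.** It opens with "Each subject must meet the following criteria to be enrolled in this study". Item 6 covers men who are not surgically sterile and asks for birth control "for a period of 30 days after discharge from the clinic". Item 7 covers women of childbearing potential and asks them to use contraception and "to not become pregnant for the duration of the study". It adds no period after discharge.
- **Section 6.7.3 (Pregnancy).** Sexually active women of childbearing potential "must use an effective method of birth control during the course of the study". The instruction to the women themselves is bounded in the same way: "During the study, all WOCBP should be instructed to contact the investigator immediately if they suspect they might be pregnant".
- **Synopsis, inclusion item 3.** "Subjects who are not surgically sterile must agree to use appropriate birth control", for the same 30 days that item 6 gives men, without regard to sex.
- **Section 6.7.4.2.** It requires that "subjects be actively monitored for SAEs for at least 14 days after discharge from the study". It says nothing about contraception and places the end of the defined study period at the last scheduled contact.

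Appendix 1 puts study termination and final discharge on Day 24 for Group 1 and Day 22 for Group 2. Group 2 takes bexagliflozin on Days 15 to 22 and is dosed on Day 22 before leaving (Section 7.3.2).

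**The concern.** The synopsis and the operative criteria give women different end dates for contraception. The operative text, which a site would apply, is the shorter. It sets a period after discharge for men but none for the women who took the drugs, and the protocol gives no reason for the difference. In Group 2 the women's duty ends on a dosing day.

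At stake is a short interval in which a woman using a barrier method could stop it, in line with the criteria, with drug still in her body. Scheduled pregnancy tests fall at screening, Day 0 and the Period 2 admission, so none follows dosing in Period 2. Section 10.4 has the consent form drafted from the protocol, so the mismatch could carry into what women are told. Women with a tubal ligation or an intrauterine device, both accepted by item 7, are not affected.

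**Working it through.** **1. When does the study end?** Section 3.3 estimates a maximum of 46 days from screening to study termination. Counting screening Days -21 to -1, Day 0, and Days 1 to 24 (Group 1) gives 21 + 1 + 24 = 46 days, which reproduces the stated figure. Group 2 gives 21 + 1 + 22 = 44 days. The 46 days leave nothing after discharge, so a duty that lasts as long as the study ends at final discharge.

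**2. How does that end relate to dosing?**

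- Group 2, last bexagliflozin dose: Day 15 + 8 - 1 = Day 22, the day of study termination.
- Group 1, last bexagliflozin dose: Day 8, which is 16 days or 384 h before Day 24. At the longer half-life, 384 / 9.71 = 39.5 half-lives have passed, so only digoxin matters.
- Digoxin, both groups: dosed 120 h before final discharge (Day 17 to 22, or Day 19 to 24).

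**3. How much exposure is left?** Section 3.2.3 gives half-lives of 7.80 to 9.71 h for bexagliflozin and about 35 h for digoxin. The cutoff is an assumption: 5 half-lives at the low end and 7 at the high end. Seven is the multiple that Section 4.3 item 7 uses for prior investigational drugs, applied here to digoxin by analogy.

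At discharge digoxin has passed 120 / 35 = 3.43 half-lives, so 2^-3.43 = 0.093, about 9%, remains.

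| Drug | Formula | 5 half-lives | 7 half-lives |
|---|---|---|---|
| Bexagliflozin (Group 2), from the Day 22 dose | k × 7.80 to k × 9.71 | 39.0 to 48.6 h (1.6 to 2.0 days) | 54.6 to 68.0 h (2.3 to 2.8 days) |
| Digoxin (both groups), after discharge | k × 35 - 120 | 55 h (2.3 days) | 125 h (5.2 days) |

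The bexagliflozin times run from the dose, so the time after leaving the clinic is slightly shorter.

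**4. How do the end dates compare?**

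| Rule | Group 1 | Group 2 |
|---|---|---|
| Item 7 and Section 6.7.3 (women) | Day 24 | Day 22 |
| 14-day monitoring for serious adverse events (Section 6.7.4.2; no contraception duty) | 24 + 14 = Day 38 | 22 + 14 = Day 36 |
| 30 days after final discharge | 24 + 30 = Day 54 | 22 + 30 = Day 52 |

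**5. How many women?** The protocol does not say. With up to 9 subjects per group, the range is 0 to 9 in Group 2 (both drugs) and 0 to 18 overall (digoxin).

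**The case against.** The strongest reply is that little turns on this. A site can satisfy both texts by applying the stricter one. Synopsis item 3 is probably an abridged form of the male criterion: it uses the same words, and read literally it also covers postmenopausal women, whom item 7 treats separately. Residual exposure is a matter of days, the 5.2-day upper end applies an investigational-drug rule to a marketed drug, and the half-lives do not justify 30 days. The documents give no reproductive-toxicity data, and the Investigator's Brochure and the consent form, which might hold more, are not among them. If the 14 days of safety monitoring counted as part of the study, exposure would be covered.

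Most of this stands, and it limits the size of the point. It does not remove it. A loosely worded synopsis is a weak basis for a safety duty that the operative list omits. The 14-day clause sets no contraception duty and treats its window as following discharge from the study. Even if those days counted, they would not match the synopsis.

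Two stronger readings are tempting and are not supported:

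- **That item 6 leaves men uncovered between periods.** Each subject is discharged twice, and item 6 does not say which discharge starts the 30 days. But if each discharge starts its own 30 days, the first runs to Day 8 + 30 = Day 38 (Group 1) or Day 6 + 30 = Day 36 (Group 2). That covers the 9 or 7 days out of the clinic, and the final discharge then runs to Day 54 or Day 52. This is an ambiguity, not a shown gap.
- **That a pregnancy after the study would go unreported.** Section 6.7.3 also requires the investigator to notify the Medical Monitor within 3 working days of learning of any subject's pregnancy, with no time limit. Only the instruction to the woman to call is bounded by the study.

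**Conclusion.** The inconsistency is real and minor. Section 4.2 item 7 and Section 6.7.3 set no contraception period for women after discharge, while item 6 and synopsis item 3 set 30 days. The uncovered exposure is about 1.6 to 2.8 days for bexagliflozin in Group 2 and 2.3 to 5.2 days for digoxin in both groups. These figures rest on the protocol's half-lives, the assumed cutoff, and reading the study as ending at final discharge, which the 46-day count and Appendix 1 support.

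A reader might infer 30 days of unprotected exposure. The documents do not support that: the 30 days is the difference between two texts, not time with drug present. No lapse or harm is shown, and the pharmacokinetic comparison is not affected. The change is worth making because it protects subjects at little cost.

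**What to change.** 1. In Section 4.2 item 7 and Section 6.7.3, require contraception from women of childbearing potential throughout the study and for 30 days after final discharge.
2. In Section 6.7.3, extend the instruction to women to report a suspected pregnancy over the same period.
3. Limit synopsis item 3 to men who are not surgically sterile and women of childbearing potential, with wording that matches Section 4.2.
4. Optionally, state in item 6 which discharge starts the men's 30 days.

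The 30 days is the sponsor's own period, already in the synopsis and item 6. It is longer than the half-lives require. A shorter period would also cover the exposure, but the synopsis would then have to change to match. Simply cutting the synopsis back to Section 4.2 as it stands would remove the conflict and leave the 2 to 5 days uncovered.

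The cost is a wording amendment, with the review board approval that Section 10.2 requires, and 30 more days of commitment for women than the body text now asks. Procedures, sample size and analysis do not change.

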4.3 Exclusion Criteria

Subjects who meet any of the following criteria will be excluded from the study.

1. Subjects who are determined by the investigator or sub-investigator to be unsuitable for participating in the study based on medical conditions or factors that would influence adherence to study activities.
2. Subjects with a clinically significant history of allergy to drugs or latex.
3. Subjects with a history of alcohol or drug dependence in the 12 months prior to the first dose.
4. Subjects who have donated 400 mL of whole blood within 56 days, 200 mL of whole blood within one month, or donated blood components within 14 days prior to first dose.
5. Subjects who have used prescription or over-the-counter (OTC) drugs within 14 days prior to the first dose.
6. Subjects who have used vitamin preparations within 7 days or supplements (including St. John's Wort and ginseng) within 14 days prior to the first dose.
7. Subjects who have been treated with an investigational drug within 30 days or 7 half-lives of the investigational drug, whichever is longer, prior to the first dose.
8. Subjects who have previously received EGT0001474 or bexagliflozin, or any other SGLT2 inhibitors within three months prior to the first dose, or have participated in previous bexagliflozin clinical trials, regardless of whether they received bexagliflozin or placebo in those trials.
9. Subject who had previously taken digoxin or drugs of the same class within 3 months prior to the first dose.
10. Subjects whose screening ECG demonstrates at least one of the following: heart rate > 100 bpm, QRS > 120 msec, QTc > 430 msec (corrected by Bazett's formula), PR > 220 msec (a subject with PR > 220 msec will generally be excluded but exceptions may be allowed at the discretion of the investigator), or any rhythm other than sinus rhythm, sinus bradycardia, or sinus arrhythmia.
11. Subjects whose sitting blood pressure is above 140/90 mmHg at screening. If the sitting blood pressure at screening is above 140/90 mmHg, one repeat measurement is allowed and the subject may be randomized if the repeat screening blood pressure is 140/90 +/-5 mmHg at the discretion of the Investigator.
12. Subjects with a heart rate <60 beats per minute.
13. Subjects with evidence of abnormal liver function tests (total bilirubin or alkaline phosphatase > 1.5 x upper limit of normal (ULN) with the exception of isolated Gilbert's syndrome); or alanine aminotransferase (ALT) or aspartate aminotransferase (AST) > 2.5 x ULN.
14. Subjects who have had a cholecystectomy.
15. Subjects with estimated glomerular filtration rate (eGFR) < 90 mL/min/1.73 m² or a history of kidney transplant.

16. Subjects who have a positive result of hepatitis B surface antigen (HBsAg), hepatitis C virus (HCV) antibody, urinary drug or urinary cotinine test.
17. Subjects with known human immunodeficiency virus (HIV) infection.
18. Subjects with a history of recurrent yeast or urinary tract infections or any such infection in the 6 months prior to the first dose.
19. Subjects who have had a febrile illness within 5 days prior to first dose.
20. Subjects vaccinated (within the exception of the flu vaccine) within 30 days prior to first dose.

5 STUDY TREATMENT(S)

5.1 Description of Treatment(s)

5.1.1 Investigational Product: Bexagliflozin

Bexagliflozin tablets, 20 mg, are blue caplet-shaped, film-coated tablets that are intended for use in investigational studies in humans. The tablets contain excipients designed to promote extended release through a gastroretentive mechanism. The active tablets exhibit a greater than 75% release of drug substance by 8 hours in simulated gastric fluid *in vitro*.

5.1.2 Cardiovascular Drug: Digoxin

Digoxin is a cardiac glycoside that mediates its effects on Na/K ATPase to increase cardiac output. Majority of digoxin is excreted in urine and bile unchanged, and metabolism of digoxin appears to be minimal (Iisalo, 1977). After oral administration, the absorption of digoxin is mediated by P-glycoprotein (P-gp). 0.25 mg digoxin tablets are white, round tablets with an imprint code JSP-545. 0.25 mg digoxin tablets are the highest available tablet dose, and two 0.25 mg tablets will be taken q.d. for this study.

5.2 Treatment(s) Administered

Each study subject will be administered 8 single oral doses of bexagliflozin tablet, 20 mg and 2 single oral doses of 0.5 mg digoxin in 2 treatment periods. See [Appendix 2](#) for the Dosing Schedule.

5.3 Selection and Timing of Dose for Each Subject

5.3.1 Bexagliflozin

After an overnight fast of at least 10 hours, subjects will take a 20 mg bexagliflozin tablet orally in the morning with approximately 240 mL of water at least 1 hour prior to drinking and 4 hours prior to eating.

5.3.2 Digoxin

After an overnight fast of at least 10 hours, subjects will take 0.5 mg digoxin orally in the morning with approximately 240 mL of water at least 1 hour prior to drinking and 4 hours prior to eating.

5.3.3 Bexagliflozin and digoxin

After an overnight fast of at least 10 hours, 0.5 mg digoxin and 20 mg bexagliflozin tablet will be co-administered orally with approximately 240 mL of water at least 1 hour prior to drinking and 4 hours prior to eating.

5.4 Method of Assigning Subjects to Treatment Groups

A total of 18 healthy subjects who consent to participate in the study will be enrolled in the study. Subjects will be randomized to one of the two study groups (Group 1 and Group 2). Subjects who discontinue the study early due to safety issues will not be replaced.

- Group 1: Treatment A first, followed by Treatment B
- Group 2: Treatment B first, followed by Treatment A

5.5 Blinding

This is an open-label study.

5.6 Concomitant Therapy

The participants are not allowed to take any prescription or non-prescription drugs or dietary supplements with the exception of acetaminophen and topical medications at any time during 14 days prior to (first) drug administration and for the duration of each study period. Vitamins are prohibited for 7 days prior to first drug administration and for the duration of the study. No other concomitant medications are permitted with the exception of those required for treatment of an adverse event. Subjects may receive any medications for adverse events that are necessary to control or minimize the likelihood of more serious adverse events in the investigators' judgment.

Concomitant medications administered at the time of randomization and during the study are to be recorded on the case report form (CRF). The medication name, dose, frequency, route of administration, date(s) of administration and reason for administration must be recorded. This documentation should continue until the end of the last study period. Medications that a subject receives after entering the study and prior to randomization must be recorded in the CRF.

5.7 Restrictions

5.7.1 Prior Therapy

No study subject shall have been dosed with any SGLT2 inhibitor within 3 months prior to the first dose of study medication, nor with an investigational drug within 30 days or 7 half-lives prior to first dose, or used any prescription medication or herbal supplements within 14 days or vitamins 7 days prior to the first dose of study medication.

